9.1.1. Estimands

9.1.1.1. Primary Estimand/Co-Primary Estimands

The primary estimand is the difference in median time (days) to sustained alleviation of all targeted COVID-19 signs and symptoms through Day 28 between PF-07321332/ritonavir and placebo in nonhospitalized adult patients with COVID-19 who are at low risk of progression to severe disease at baseline and were treated ≤ 5 days after COVID-19 symptom onset. This will be estimated irrespective of adherence to randomized treatment. Because the study did not meet the primary endpoint based on the interim analysis at 45%, all hypothesis assessments are done with a nominal alpha.

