9.2. Analysis Sets

For purposes of analysis, the following analysis sets are defined:

Participant Analysis Set	Description
Full Analysis Set (FAS)	All participants randomly assigned to study intervention regardless of whether or not study intervention was administered.
Safety Analysis Set (SAS)	All participants randomly assigned to study intervention and who take at least 1 dose of study intervention. Participants will be analyzed according to the study intervention they received. A randomized but not treated participant will be excluded from the safety analyses.
Modified Intent -To-Treat (mITT)	All participants randomly assigned to study intervention who take at least 1 dose of study intervention and with at least 1 postbaseline visit through Day 28 who were treated ≤ 3 days after COVID-19 symptom onset. Participants will be analyzed according to the study intervention to which they were randomized.
Modified Intent -To-Treat 1 (mITT1)	All participants randomly assigned to study intervention, who take at least 1 dose of study intervention. Participants will be analyzed according to the study intervention to which they were randomized.
Per-Protocol (PP)	All participants in the mITT1 set without major protocol violations considered to impact the interpretation of the primary efficacy endpoint. Protocol deviations will be reviewed to generate the list of participants with significant deviations to be excluded from the PP analysis set. The PP exclusion criteria will be finalized prior to breaking the blind.

Both the mITT1 and PP analysis sets will be used in the analyses of the primary efficacy endpoint, with the mITT1 being primary. For proportion of COVID-19-related hospitalization or death from any cause endpoint, mITT1 will be used. For all other efficacy analysis, the mITT1 analysis set will be used, as defined in the SAP. The Safety Analysis Set will be used in the analyses of the safety data.

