Third interim analysis (100% planned enrollment through Protocol Amendment 4): A third interim analysis was completed on enrolled participants who had risk factors for severe COVID-19 illness (ie, vaccinated against the SARS-CoV-2 virus) as well as participants who did not have risk factors for severe COVID-19 illness (ie, not vaccinated). Data from the study are required to support regulatory submissions thereby necessitating an interim analysis utilizing the 19 December 2021 dataset. This dataset had not been analyzed previously because the protocol was amended to increase the sample size and extend enrollment to assess the potential benefit of participants at low risk of progression to severe COVID-19 in the clinically relevant endpoint of hospitalization or death (Protocol Amendment 5, 21 January 2022). The participants who were vaccinated are considered the high risk population and the unvaccinated participants are considered standard risk in the statistical analysis.

There was no adjustment for alpha for this third interim analysis. Nominal p-values will be reported. This third interim analysis did not include any data from participants who entered the study under Protocol Amendment 5.

Before the third interim analysis was performed, the details of the objectives, dissemination plan, method of maintaining the study blind, and the analysis details as per Pfizer's SOPs will be documented and approved in the interim CSR analysis plan.

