2.1.2. Secondary Estimands

The estimands associated with the secondary objectives are as follows:

- *The difference in proportions of patients experiencing COVID-19-related hospitalization or death from any cause through Day 28 in nonhospitalized adult patients with COVID-19 who are at low risk of progression to severe disease and were treated ≤ 5 days after COVID-19 symptom onset. This will be estimated without regard to adherence to randomized treatment.*
- *The difference in estimated rate of number of COVID-19-related medical visits through Day 28 in nonhospitalized adult patients with COVID-19 who are at low risk of progression to severe disease at baseline. This will be estimated irrespective of adherence to randomized treatment.*
- *The difference in the estimated rate of number of days in hospital and ICU stay in patients with COVID-19-related hospitalization through Day 28 in nonhospitalized adult patients with COVID-19 who are at low risk of progression to severe disease and were treated ≤ 5 days after COVID-19 symptom onset. This will be estimated without regard to adherence to randomized treatment.*

Estimands for the other outcome measures are not presented.

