- First interim analysis (45% planned enrollment through Protocol Amendment 4): A planned interim analysis for efficacy, futility and sample size reestimation was conducted after approximately 45% of participants completed the Day 28 assessments in the mITT analysis set.
- Second interim analysis (80% planned enrollment through Protocol Amendment 4): At the request of the E-DMC, a second interim analysis was conducted on 80% of enrolled participants without any adjustment to the alpha.
- Third Interim analysis (100% planned enrollment through Protocol Amendment 4): A third interim analysis was completed on enrolled participants who had risk factors for severe COVID-19 illness (ie, vaccinated against the SARS-CoV-2 virus) as well as participants who did not have risk factors for severe COVID-19 illness (ie, not vaccinated). Data from the study were required to support regulatory submissions thereby necessitating an interim analysis utilizing the 19 December 2021 dataset. This dataset had not been analyzed previously because the protocol was amended to increase the sample size and extend enrollment to assess the potential benefit of

participants at low risk of progression to severe COVID-19 in the clinically relevant endpoint of hospitalization or death (Protocol Amendment 5, 21 January 2022). The participants who were vaccinated were considered the high risk population and the unvaccinated participants were considered standard risk in the statistical analysis. This interim analysis was without any adjustment to the alpha.

Subsequent to the interim analyses above, there will be a final analysis for reporting the results of this study. The final study analysis will be performed after all participants have completed or otherwise withdrawn from the study. The study schematic is provided in Figure 1.

Figure 1. Schema

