4. ANALYSIS SETS (POPULATIONS FOR ANALYSIS)

Data for all participants will be assessed to determine if participants meet the criteria for inclusion in each analysis population prior to unblinding and releasing the database and classifications will be documented per standard operating procedures.

Population	Description
Full Analysis Set (FAS)	All participants randomly assigned to study intervention regardless of whether or not study intervention was administered.
Safety Analysis Set (SAS)	All participants who receive at least 1 dose of study intervention. Participants will be analyzed according to the intervention they actually received. A randomized but not treated participant will be excluded from the safety analyses.

Population	Description
Modified Intent -To Treat (mITT)	All participants randomly assigned to study intervention who take at least 1 dose of study intervention and with at least 1 postbaseline visit through Day 28 who were treated ≤ 3 days after COVID symptoms onset. Participants will be analyzed according to the study intervention to which they were randomized.
Modified Intent-To-Treat (mITT1)	All participants randomly assigned to study intervention, who take at least 1 dose of study intervention. Participants will be analyzed according to the study intervention they were randomized.
Per-Protocol (PP)	All participants in the mITT1 set without important protocol deviations considered to impact the interpretation of the primary efficacy endpoint. Protocol deviations will be reviewed to generate the list of participants with significant deviations to be excluded from the PP analysis set. The PP exclusion criteria will be finalized prior to breaking the blind.

Both the mITT1 and PP analysis sets will be used in the analyses of the primary efficacy endpoint, with the mITT1 being primary. For proportion of COVID-19 related hospitalization or death from any cause and all other efficacy endpoints, mITT1 will be used. The Safety Analysis Set will be used in the analyses of the safety data.

Multiple Enrollers:

If a participant enters/is randomized into Study C4671002 more than once or is enrolled in Study C4671002 and in 1 or 2 other Phase 2/3 nirmatrelvir/ritonavir studies:

- (1) The primary and key secondary efficacy analyses will be performed by considering all enrolled participants (subject IDs) as independent participants.

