6.2.2. Incidence of SAEs and AEs Leading to Discontinuations

The incidence of SAEs and AEs leading to discontinuation will be summarized by treatment group using the SAS population.

6.2.3. Proportion of Participants with COVID-19 Related Hospitalization or Death From Any Cause Through Day 28

The estimand for proportion of participants experiencing COVID-19 related hospitalization or death from any cause through Day 28 is the difference in proportions of participants experiencing COVID-19 related hospitalization or death from any cause through Day 28 in nonhospitalized adult patients with COVID-19 who are at low risk of progression to severe disease and were treated ≤ 5 days after COVID-19 symptom onset. This will be estimated irrespective of adherence to randomized treatment.

The statistical methodology for proportion of participants with COVID-19 related hospitalization or death from any cause through Day 28 will be as follows:

The cumulative proportion of participants hospitalized for the treatment of COVID-19 or death during the first 28 days of the study will be estimated for each treatment group using the Kaplan-Meier method to take account of lost to follow-up and summarized graphically for each treatment group. The estimand is the difference of the proportions in the 2 groups and its 95% CI will be presented, as well as, the associated two sample proportion test (Wald test results). For the 95% CI, the corresponding estimate of the standard error is computed using Greenwood's formula⁴. The Greenwood's formula to estimate the variance of the difference of proportions at Day 28 is $[\text{Var}(S_{PF}(28)) + \text{Var}(S_{\text{Placebo}}(28))]$. Instead of dealing with $S(t_i)$ the log-log approach to CI will be used. The 95% CI will be computed for the estimate of $L(t) = \log(-\log(S(t)))$, the log hazard function.

The CI will be in the right range when transformed back to $S(t) = \exp(-\exp(L(t)))$. Antilogging this CI will give a 95% confidence interval for the difference itself.

A sensitivity analysis for proportion of participants with COVID-19 related hospitalization or death from any cause through Day 28 will be provided using mITT1 as follows:

For participants with missing data due to lost to follow up for COVID-19 related hospitalization or death from any cause, the sensitivity analysis will implement the following event imputation methodology for those with missing data:

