6.4. Subset Analyses

Subgroup analyses of the primary endpoint and key secondary endpoint (hospitalization due to COVID-19 and death of any cause) will only be performed for vaccination status and others will be analyzed if necessary for post hoc. The subgroup variables include:

- Age group (<65, ≥ 65);
- Sex;
- Race;
- Vaccination status. The vaccination subgroup is defined as follows:
 - a) Participant who enrolled prior to PA #5 and were completely vaccinated are considered high risk group.
 - b) Participants who enrolled prior to PA#5 and were not vaccinated, plus all participants enrolled after implementation of PA#5 are considered as standard risk group.
- Baseline serology (PCR positive, PCR negative);
- Baseline viral load defined as: <10⁴ copies/mL vs ≥10⁴ copies/mL;
- Maximum severity of targeted baseline signs and symptoms (mild, moderate, severe)
- Vaccination status and by maximum severity of targeted baseline signs and symptoms (mild, moderate, severe)
- Baseline viral load defined as: <10⁷ copies/mL vs ≥10⁷ copies/mL;
- BMI category (<30, ≥30);
- Type of COVID-19 variant (i.e., Omicron, BA2);
- Baseline Comorbidities:
 - Smoking;

- Chronic lung disease requiring medication;
- Hypertension (taking medications for hypertension);
- Cardiovascular disorders;
- Diabetes (taking medications for diabetes) for safety reporting;
- Chronic kidney disease;
- Sickle cell disease;
- Neurodevelopmental disorders;
- Cancer other than localized skin cancer;
- Medical-related technological dependence.

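### The primary and key secondary estimands name low-risk patients, but the lead analysis set (mITT1) also contains the pre-Amendment 5 vaccinated participants whom the plan labels high risk

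*SAP*

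**What the plan says.** **Estimands.** Protocol 9.1.1.1 states the primary estimand "in nonhospitalized adult patients with COVID-19 who are at low risk of progression to severe disease at baseline", and SAP 2.1.1 agrees. The estimand for hospitalization or death is set in the same kind of patient in protocol 9.1.1.2, in SAP 2.1.2 ("who are at low risk of progression to severe disease") and again in SAP 6.2.3 ("in nonhospitalized adult patients with COVID-19 who are at low risk of progression to severe disease and were treated").

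**Lead analysis set.** Protocol 9.2 and SAP 4 make mITT1 primary for the symptom endpoint. For the key secondary endpoint the protocol says "For proportion of COVID-19-related hospitalization or death from any cause endpoint, mITT1 will be used" and the SAP says "For proportion of COVID-19 related hospitalization or death from any cause and all other efficacy endpoints, mITT1 will be used". mITT1 is defined by randomisation and at least one dose, with no condition on risk, vaccination or amendment.

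**Risk labels.** Protocol 9.4 says "The participants who were vaccinated are considered the high risk population and the unvaccinated participants are considered standard risk in the statistical analysis"; SAP 2.2 repeats this. SAP 6.4(a) applies the high-risk label to completely vaccinated participants enrolled before Amendment 5, and 6.4(b) defines the complement: "Participants who enrolled prior to PA#5 and were not vaccinated, plus all participants enrolled after implementation of PA#5 are considered as standard risk group". SAP 3.5, by contrast, ties the labels to vaccination status alone: completely vaccinated is high risk, not vaccinated is standard risk.

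**Planned subgroup results.** SAP 6.4 commits to subgroup analyses of both endpoints by vaccination status. Appendix 1 lists a Cox model for the primary endpoint and the Kaplan-Meier method for the key secondary.

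**The concern.** Followed as written, the plan gives a lead estimate for a mixed-risk population and reports it under an estimand for low-risk patients. Amendment 5 extended enrolment in order to assess benefit in low-risk participants, so a reader will take the lead estimate as the answer to that question.

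The key secondary estimand is an absolute difference in proportions. Even if the relative effect were the same in both risk groups, that difference would depend on how many high-risk participants are in the set and on their event rate.

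There is a second, smaller point. Exclusion 16 bars vaccination only within 12 months of screening, and the Amendment 5 rationale expects some participants vaccinated earlier than that. Such a person, if completely vaccinated, is high risk under SAP 3.5 and standard risk under SAP 6.4. Vaccination is a term in the Cox and covariate models (SAP 5.2, 5.2.2, 6.1.1.2, 6.2.13) and defines the subgroup, so conflicting codes can reach those analyses. The unadjusted lead Kaplan-Meier analyses are not affected.

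**Working it through.** **The plan's own sample size reproduces** (protocol 9.5, SAP 2.3)
- 1140 + 740 = 1880.
- 1880 / 0.95 = 1979, stated as about 1980.

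All 1140 earlier participants are counted in the 1880, so the 26 events and the conditional power of about 90% refer to the pooled sample.

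**Share of the lead set labelled high risk**
- Input: about 60% of participants enrolled at the time had risk factors and were vaccinated (Amendment 4 rationale, protocol 10.11). The final share is not given. I assume 60% for all 1140, with 50-70% as a range.
- High-risk number = share x 1140.

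| Share | High risk | Of 1880 | Standard risk |
|---|---|---|---|
| 50% | 570 | 30% | 1310 |
| 60% | 684 | 36% | 1196 |
| 70% | 798 | 42% | 1082 |

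**How far the pooled and standard-risk differences could lie apart (illustration, key secondary endpoint)**
- Assumptions: 26 events in total, 1:1 allocation, a 70% reduction, and the 1.5% event rate read as the overall rate in the added 740.
- Events from the added participants: 740 x 0.015 = 11.1. Events left for the 1140: 26 - 11.1 = 14.9.
- With a rate ratio of 0.3, placebo has 1/1.3 = 10/13 of events and active 3/13. The difference is events x (7/13) / participants per arm.
- Pooled: 26 x (7/13) / 940 = 1.49 percentage points.
- Standard risk at a 60% share, with equal event risk in the two groups of the 1140: events = 11.1 + 0.4 x 14.9 = 17.1; difference = 17.1 x (7/13) / 598 = 1.54 points. The gap is about 0.05 points.
- If high-risk event risk is r times low-risk: standard-risk events = 11.1 + 14.9 x 0.4 / (0.4 + 0.6r). For r = 3 this is 13.8 events and 1.24 points; for r = 1/3 it is 21.0 events and 1.89 points. No passage supports either value of r; they show only that the sign can go either way.
- If 1.5% is instead a placebo rate: 370 x 0.015 x 1.3 = 7.2 events from the added participants, 26 - 7.2 = 18.8 from the 1140, and 7.2 + 0.4 x 18.8 = 14.7 standard-risk events. The difference is then about 1.3 points, below the pooled figure even with equal risk in the 1140.

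**Precision in the standard-risk group**
- 95% half-width = 1.96 x sqrt[p1(1-p1)/n + p2(1-p2)/n], a simple Wald form standing in for the planned Kaplan-Meier interval.
- Pooled: p1 = 20/940, p2 = 6/940, half-width 1.05 points.
- Standard risk, central case: p1 = 13.1/598, p2 = 3.9/598, half-width 1.34 points.

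The wider interval is ordinary subgroup imprecision. It is not a measure of the mismatch, but it is what a reader needs in order to interpret the low-risk result.

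**Primary endpoint.** No medians by risk group are given, so no size can be put on it.

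**The case against.** **Low risk may be only a study-level label.** Protocol 4.1 applies it to all 1980 or so participants, and protocol 4.2 reads first-interim data, which predate Amendment 5, as bearing on low-risk patients. On this view high and standard risk are merely analysis strata. That supports treating the matter as one of definition, but it does not remove the conflict. Current Exclusion 1 lists the risk factors as raising the risk of severe illness and makes no exception for vaccination, and both documents label the vaccinated group high risk.

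**The standard-risk result is largely planned.** This stands for the key secondary endpoint, where Appendix 1 lists a Kaplan-Meier analysis by vaccination status. For the primary endpoint the listed Cox model gives a hazard ratio, not the difference in medians that the estimand names. No visible passage ties either row to the estimand. The Appendix 1 footnote defines Pre-PA5 and Post-PA5 sets that redacted rows may use. Post-PA5 is in any case not the SAP 6.4(b) group, which also takes in the unvaccinated participants enrolled earlier.

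**The conflicting codes may be rare or absent.** The documents do not say whether someone vaccinated at least 12 months earlier was recorded as completely vaccinated. So a participant can get conflicting codes; that anyone did is not shown, and the number is not given.

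**No confirmatory claim is at stake.** The primary endpoint was not met at the first interim analysis and all remaining analyses are nominal. This limits the severity. But the stated purpose of the key secondary analysis is now a point estimate and interval, so the population described is most of what it conveys.

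**Conclusion.** The mismatch holds as a matter of text: low-risk estimands, a lead set with no risk restriction, and a labelled high-risk group inside it. On the assumption that the Amendment 4 share of about 60% applied to all 1140, about 36% of the 1880 are high risk (30-42% for 50-70%). The finding itself does not depend on that share. It should be fixed, but it concerns which population the estimates describe.

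Three stronger readings are tempting, and the documents support none of them.
- That pooling inflates, or dilutes, the apparent benefit in low-risk patients. Events are not split by risk group. The gap is about 0.05 points if event risks are equal within the 1140 and 1.5% is an overall rate, and it can take either sign otherwise.
- That the conditional power of about 90% is wrong. It rests on second-interim data that are not given, so it can be neither checked nor faulted; all that can be said is that it refers to the pooled sample.
- That the plan has no low-risk analysis. It has one for the key secondary endpoint, as a subgroup not linked to the estimand.

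**What to change.** 1. **Keep mITT1 as the lead set.** Interim results by arm have been seen (protocol 4.2, 9.4), so the lead population should not be switched now. State the estimand population as all participants randomised and dosed across amendments, that is, standard-risk participants plus vaccinated participants with risk factors. Describing it by type of patient, not by enrolment date alone, keeps it interpretable. Beside each lead estimate report the SAP 6.4(b) standard-risk estimate with its 95% CI, as nominal and descriptive, and base statements about low-risk patients on it. For the primary endpoint add Kaplan-Meier medians and their difference by risk group to Appendix 1.
2. **Use one risk-group variable**, defined as in SAP 6.4. Keep vaccination status as randomised as a separate variable, and align SAP 3.5, 5.2, 6.1.1.2 and 6.4. Report how many participants differ between the two.
3. **In protocol 9.5 and SAP 2.3**, state that the 26 events and the conditional power of about 90% refer to the pooled 1880, and that precision for the standard-risk group is lower.

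**Cost.** Wording in the estimand, analysis and sample-size sections of both documents, one small extra output, and no more patients. The price is that the lead estimate openly no longer answers the low-risk question alone.

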17. Is unwilling to abstain from participating in another interventional clinical study with an investigational compound or device, including those for COVID-19 therapeutics, through the long-term follow-up visit. Previous administration with any investigational drug or vaccine within 30 days (or as determined by the local requirement) or 5 half-lives preceding the first dose of study intervention used in this study (whichever is longer).
18. Known prior participation in this trial or other trial involving PF-07321332.

Diagnostic Assessments:

19. Known history of any of the following abnormalities in clinical laboratory tests (within past 6 months of the screening visit):
 - AST or ALT level ≥ 2.5 X ULN;
 - Total bilirubin ≥ 2 X ULN (≥ 3 X ULN for Gilbert's syndrome);
 - eGFR < 45 mL/min/1.73 m² within 6 months of the screening visit, using the serum creatinine-based CKD-EPI formula;²⁸
 - Absolute neutrophil count < 1000 /mm³.

Note: If the investigator suspects the participant may have any of the above laboratory values, confirmatory tests should be performed at screening to confirm eligibility before the first dose of study intervention. See [Appendix 2](#) for more details.

20. Oxygen saturation of $< 92\%$ on room air obtained at rest within 24 hours prior to randomization.

NOTE: For a potential participant who regularly receives chronic supplementary oxygen for an underlying lung condition, oxygen saturation should be measured while on their standard home oxygen supplementation.

Other Exclusions:

21. Females who are pregnant or breastfeeding.
22. Investigator site staff or Pfizer employees directly involved in the conduct of the study, site staff otherwise supervised by the investigator, and their respective family members.

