- (2) Sensitivity analyses for both the primary and key secondary endpoints will be performed using only data from a duplicate participant's first enrollment within this study and excluding data from a duplicate participant's subsequent enrollments.

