9. APPENDICES

Appendix 1. Summary of Efficacy Analyses

Endpoint	Analysis Type	Population	Data Inclusion and Rules for Handling Intercurrent Events and Missing Data	Analysis Model
Time (days) to sustained alleviation of all targeted COVID-19 signs/symptoms through Day 28.	Primary efficacy Analysis	mITT1	All data collected will be included. Missing severity at baseline will be treated as mild. Other missing data will be estimated with KM (lifetest) procedure	Kaplan-Meier & Log rank test
Time (days) to sustained alleviation of all targeted COVID-19 signs/symptoms through Day 28.	Sensitivity analysis for primary endpoint	mITT1	All data collected will be included. Missing severity at baseline will be treated as mild.	Cox proportional hazard model
Time (days) to sustained alleviation of all targeted COVID-19 signs/symptoms through Day 28.	Sensitivity analysis for primary endpoint	mITT1 exclude site 1488	All data collected will be included. Missing severity at baseline will be treated as mild.	Cox proportional hazard model
Time (days) to sustained alleviation of all targeted COVID-19 signs/symptoms through Day 28.	Supplemental analysis for primary endpoint	PP	Participants who discontinued the study before Day 28 without event will be censored at Day 25.	Kaplan-Meier & Log rank test
Time (days) to sustained alleviation of all targeted COVID-19 signs/symptoms through Day 28.	Sensitivity analysis for Primary Efficacy analysis for multiple enrollers	mITT1 including only data with first randomization within the study	All data collected will be included regardless of intercurrent events. Kaplan-Meier method to take account of losses to follow-up.	Kaplan-Meier method
Time (days) to sustained alleviation of all targeted COVID-19 signs/symptoms through Day 28 by vaccination status	Subgroup analysis for primary endpoint	mITT1	Use baseline variables as described in Section 6.4.	Cox proportional hazard model
Proportion of participants with COVID-19 related hospitalization or death from any cause through Day 28	Key secondary analysis	mITT1	All data collected will be included regardless of intercurrent events. Kaplan-Meier method to take account of losses to follow-up.	Kaplan-Meier method

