Proportion of participants with COVID-19 related hospitalization or death from any cause through Day 28	Sensitivity analysis for key secondary endpoint	mITT1	If the participant's last observed data is prior to Day 21, then impute as an event with event day as day of last observed data +1. If the participant's last observed data is on or after Day 21, do not impute an event and	Kaplan-Meier method

Endpoint	Analysis Type	Population	Data Inclusion and Rules for Handling Intercurrent Events and Missing Data	Analysis Model
			participant remains censored at day of last observed data.	
Proportion of participants with COVID-19 related hospitalization or death from any cause through Day 28	Sensitivity analysis for key secondary efficacy analysis for multiple enrollers	mITT1 including only data with first randomization within the study	All data collected will be included regardless of intercurrent events. Kaplan-Meier method to take account of losses to follow-up.	Kaplan-Meier method
Proportion of participants with COVID-19 related hospitalization or death from any cause through Day 28 by vaccination status	Subgroup analysis for key secondary endpoint	mITT1	Subset analysis identified in Section 6.4.	Kaplan-Meier method
Proportion of participants with COVID-19 related hospitalization or death from any cause through Day 28	Supplemental analysis for key secondary efficacy endpoint	PP	Participants who discontinued the study before Day 28 without event will be censored at Day 25.	Kaplan-Meier & Log rank test
Proportion of participants with death (all cause) through Week 24.	Secondary analysis	mITT1	All data collected will be included regardless of intercurrent events exclude participants enrolled under PA6	Logistic Regression
Number of COVID-19 related medical visits through Day 28.	Secondary analysis	mITT1	All data collected will be included regardless of intercurrent events. Missing data will not be imputed.	Descriptive statistics (based on negative Binomial Model)
Number of days in hospital and ICU stay in participants with COVID-19 related hospitalization through Day 28.	Secondary analysis	mITT1	All data collected will be included regardless of intercurrent events. Missing data will not be imputed.	Descriptive statistics
Proportion of participants with severe signs/symptoms attributed to COVID-19 through Day 28.	Secondary Efficacy Analysis	mITT1	All data collected will be included regardless of intercurrent events, LOCF for missing data.	Logistic regression model

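### The sensitivity analysis for multiple enrollers removes repeat randomizations within C4671002 but not people who entered another trial of the drug first

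*SAP*

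**What the plan says.** Protocol Section 5.2, Exclusion 18, bars "Known prior participation in this trial or other trial involving PF-07321332".

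SAP Section 4, under Multiple Enrollers, covers people who got in more than once all the same. It names two groups: those randomized into C4671002 more than once, and anyone who "is enrolled in Study C4671002 and in 1 or 2 other Phase 2/3 nirmatrelvir/ritonavir studies". Two rules follow.

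- Item (1): the primary and key secondary analyses are run by "considering all enrolled participants (subject IDs) as independent participants".
- Item (2): sensitivity analyses for both endpoints use only data from a repeat enroller's "first enrollment within this study and excluding data from a duplicate" participant's later entries.

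SAP Appendix 1 repeats item (2) in two rows, one per endpoint. The population is "mITT1 including only data with first randomization within the study", and the row for hospitalization or death is labelled "Sensitivity analysis for key secondary efficacy analysis for multiple enrollers".

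On the per-protocol (PP) set, SAP Section 4 lists no specific exclusions. It says only that deviations will be reviewed and that "The PP exclusion criteria will be finalized prior to breaking the blind".

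**The concern.** The rule defines its target as two groups, but the check built on it acts on only one. Restricting to the first enrolment within this study removes second and later records of people randomized here more than once. It does nothing to a person whose other enrolment was in a different trial, because that person has only one record here.

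The people left untouched are those who entered another trial of the drug before C4671002. They fall under Exclusion 18 if the earlier participation was known. Depending on timing, they may also fall under Exclusion 17 (an investigational drug within 30 days or 5 half-lives, whichever is longer). If the earlier trial treated a separate confirmed infection, as C4671005 required, Exclusion 5 is in play as well. Such a person could bring earlier active drug, or immunity from an earlier infection, into either arm.

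What is at stake is how the check will be read. A statement that results were unchanged after accounting for multiple enrollers would be taken to cover both groups, when the second had not been examined.

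**Working it through.** **Step 1. Apply the rules to each kind of multiple enroller.**

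| Enrolment history | Records in C4671002 | Main analysis | Sensitivity analysis as written | If restricted to first enrolment across the trials |
|---|---|---|---|---|
| C4671002 twice, no other trial | 2 | both kept | first kept, second dropped | same as written |
| Another trial first, then C4671002 once | 1 | kept | kept | dropped |
| C4671002 first, then another trial | 1 | kept | kept | kept |
| Another trial first, then C4671002 twice | 2 | both kept | first kept, second dropped | both dropped |

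The second row is the gap: main and sensitivity analyses use the same record. One might try to read the later-enrolment wording in item (2) as covering a C4671002 record that follows another trial. The same sentence keeps the first record within this study, and both Appendix 1 rows say first randomization within the study, so that reading fails.

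**Step 2. Look for another analysis that covers the gap.** The Cox model, the analysis without Site 1488, the Day 25 censoring rule and the Day 21 event imputation address other questions. The PP analyses could cover it, but no text says that an Exclusion 18 breach removes a participant from PP.

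**Step 3. Gauge the size on the key secondary endpoint.** The plan states no figure on this point, so this is an illustration.

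Inputs from Protocol Section 9.5: 26 events, a 70% reduction, and 1140 + 740 = 1880 participants. The plan's enrolment figure reproduces: 1880 / 0.95 = 1979, against about 1980 stated. With 1:1 allocation, 1880 / 2 = 940 per arm. Splitting 26 events in the ratio 0.3 : 1 gives 26 × 0.3 / 1.3 = 6 active and 20 placebo.

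For a active and b placebo events, let p1 = a/940 and p2 = b/940. The difference is d = p1 − p2, its SE is √[p1(1−p1)/940 + p2(1−p2)/940], and the 95% CI is d ± 1.96 SE. This simple Wald interval stands in for the planned Kaplan-Meier method.

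| Events, active v placebo | Difference (points) | 95% CI |
|---|---|---|
| 6 v 20 (planned effect) | -1.49 | -2.54 to -0.44 |
| 6 v 19 | -1.38 | -2.42 to -0.35 |
| 6 v 18 | -1.28 | -2.29 to -0.26 |
| 8 v 18 (borderline) | -1.06 | -2.12 to -0.01 |
| 8 v 17 (one placebo event removed) | -0.96 | -1.99 to +0.08 |
| 7 v 18 (one active event removed) | -1.17 | -2.20 to -0.14 |

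Worked for 8 v 17: p1 = 0.00851, p2 = 0.01809, d = -0.00957, SE = 0.00528, and 1.96 × SE = 0.01035. Using 939 in the placebo arm gives the same limits to two decimals.

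At the planned effect, removing one or two placebo events leaves the interval clear of 0. At a borderline split, removing one placebo event changes whether it includes 0. Removing one active event moves it the other way.

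**The case against.** The strongest reply is that little is wrong. The mITT1 set is defined as randomized and dosed participants, so keeping people who turn out to be ineligible is what it is meant to do. Exclusion 18 covers known participation, and an analysis rule for people who entered despite it does not contradict it. PP analyses are planned for the primary endpoint and, in Appendix 1, for hospitalization or death. The deviation review behind them could catch these people. No alpha remains and all further p-values are nominal. All of this stands, and it limits the point to the incomplete check.

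A reader might infer more than the documents support:

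- **Double counting and understated variance.** These arise only for people randomized more than once in C4671002, whom item (2) already reduces to one record. A cross-trial enroller has one record here and cannot supply two events. Even for within-study repeats the effect is modest. With m people each counted twice in the same arm and perfectly correlated outcomes, the SE is understated by a factor √(1 + 2m/1880), which is 1.003 for an assumed m = 5 and 1.042 for m = 80.
- **Exclusion 5 for the same illness.** That criterion concerns confirmed infection before the current episode, so it does not reach a person treated elsewhere for the same episode.
- **A known share of the problem left untested.** No counts are given. Nor is the order of enrolments, and if C4671002 came first, no earlier trial exposure arises and the existing rule is adequate.
- **A false benefit.** Earlier active drug in placebo participants would tend to dilute the effect, and it requires active treatment elsewhere close enough in time to matter.

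**Conclusion.** The point holds in a limited form. The sensitivity analysis for multiple enrollers handles one of the two groups that the SAP itself names. For people who entered another trial of the drug before entering C4671002 once, it equals the main analysis by construction. The issue is ineligibility and possible earlier exposure or infection. The main analysis is not at fault, and the PP analyses may remove some of these people, but the SAP does not say so.

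The effect is probably small. On the key secondary endpoint it could decide whether the nominal interval excludes 0 only if the result is borderline, as in the 8 v 18 against 8 v 17 illustration. That rests on assumed event splits, 940 per arm, a Wald interval, and at least one such person having an event; none of these is an observed figure. On the primary endpoint, planned on about 515 events, a few records are unlikely to move the result. This is a cheap improvement, not a threat to the trial's conclusions.

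**What to change.** - In SAP Section 4, item (2), and in the two multiple-enroller rows of Appendix 1, keep a C4671002 record only if it is the participant's first enrolment across this study and the other Phase 2/3 nirmatrelvir/ritonavir studies.
- Report the number of multiple enrollers by arm and by type: repeat within this study, another trial first, this trial first.
- State before unblinding whether an Exclusion 18 breach removes a participant from the PP set.

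The new restriction selects on a fact settled before randomization into the record concerned. The rule already presupposes that cross-trial enrollers can be identified. The cost is one changed clause and a few participants fewer in a sensitivity analysis; the main analysis is unchanged.
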